8.2. Sample size and power calculation

Each arm will contain 18 participants, for a total of 36 participants. In previous work, we observed a change from baseline in SFGS of 9.4 with a standard deviation of 7.1 and intra-subject correlation of pre-post measurements of 0.86. Assuming the same standard deviation, a correlation of 0.5, and a loss of follow up of 10%, with a mean treatment difference of 7 points between arms, the planned sample size will provide approximately 80% power.

Patients will be recruited from the Facial Nerve Clinic at the University of Wisconsin Hospitals and Clinics. This is a high-volume tertiary care center with approximately 6 new synkinesis patients per clinic, making our pool of eligible participants approximately 72 patients per year. With an accrual goal of 36 participants within 1 year, we would need to recruit 50% of eligible patients over the year.

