Neuromuscular retraining is a type of physical therapy that strives to improve coordination among synkinetic facial muscles by enhancing neural adaptation and motor learning. Therapy is a comprehensive program that includes patient education, sensory feedback (including surface electromyography, proprioceptive and mirror feedback), and at home practice of minimal, precisely coordinated movements. The goal of neuromuscular retraining is to improve motor patterns in much the same way as learning to play piano or other fine motor skill, through individualized home daily practice. It is distinguished from non-specific therapies in that it does not use gross motor, maximum effort exercises or electrical stimulation, which can reinforce abnormal movement patterns. A seminal controlled trial in 1991 showed that neuromuscular retraining, which includes monthly retraining visits and a structured home rehabilitation program, was efficacious in a small group of patients with long-standing synkinesis. More recently, therapy was shown to decrease oral synkinesis stimulated by brow or ocular motion in an uncontrolled cohort study.

Our team recently completed a retrospective cohort analysis of 53 consecutive facial synkinesis patients seen at the UW *Facial Nerve Clinic* from 2012-2016, with a cohort evaluated at least 4 months after onset of paralysis to the first therapeutic encounter and in patients who underwent at least 3 months of retraining therapy. The patient-reported Synkinesis Assessment Questionnaire (SAQ) and clinician-reported Sunnybrook Facial Grading System (SFGS) were administered before and after therapy finding a small mean improvement (and large variation) on the patient-reported SAQ of 3.9 (SD 24.0, $p=0.25$) from baseline SAQ score 64.4 (IQR 46.7-80.0). However, our UW team of clinicians recorded clinically and statistically significant mean improvement of 9.4 (SD=7.1, $p < 0.001$) from baseline SFGS score 53.0 (IQR=47.0-67.0). While these retrospective data are subject to bias, the trends support our hypothesis that neuromuscular retraining therapy is efficacious for the treatment of synkinesis on the clinician-reported SFGS. The data also supported a secondary hypothesis that our current patient-reported instrument does not adequately capture the patient condition before or after treatment.

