8.1. Statistical Analysis

The primary endpoint is the clinician-evaluated SFGS. We will compare the pre-post change (at baseline and 4 months) in SFGS between the treatment arms. Statistical analyses will be based on a treatment difference relative to baseline at 4 months in a linear random effects model with: a group difference at baseline, a time (0/1) variable indicating 4 months versus baseline, a group-by-time interaction representing the treatment difference, and a random effect at the subject level.

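### Section 8.2 combines an SD of change observed at correlation 0.86 with an assumed correlation of 0.5, so the stated 80% power is not supported at 0.5

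*Combined protocol and SAP*

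**What the plan says.** Section 8.2 of the combined protocol and SAP takes its variability from the clinic's earlier cohort: "we observed a change from baseline in SFGS of 9.4 with a standard deviation of 7.1", together with an "intra-subject correlation of pre-post measurements of 0.86". Section 1.1 confirms that 7.1 belongs to the change, reporting a "mean improvement of 9.4 (SD=7.1") "from baseline SFGS score 53.0 (IQR=47.0-67.0").

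The planning sentence in section 8.2 then reads "Assuming the same standard deviation, a correlation of 0.5, and a loss of follow up of 10" percent. With a 7-point difference between arms it gives power of approximately 80% for the planned size: "Each arm will contain 18 participants, for a total of 36 participants". It does not say whether the SD is that of the change or of a single score. Alpha and sidedness are not stated.

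The primary test in section 8.1 is a linear random effects model on baseline and 4-month scores, with "a group-by-time interaction representing the treatment difference, and a random effect at the subject level".

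**The concern.** With two time points and complete data, the group-by-time interaction in section 8.1 is the difference between arms in mean change. The pre-post correlation therefore affects power only through the SD of change. An SD of change of 7.1 observed at 0.86 already reflects that high correlation. Lowering the correlation to 0.5 and leaving 7.1 in place either has no effect on the calculation or quietly assumes scores about half as variable as those in the earlier cohort.

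This sentence is the only justification for 36 participants. Replacing an observed 0.86 with 0.5 is easily read as a cautious choice. If it gives no protection, a reader is misled about how far power depends on the trial reaching a correlation as high as the earlier cohort's.

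**Working it through.** **Inputs**

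- 18 per arm, 10% loss, difference 7, assumed correlation 0.5 (section 8.2).
- SD of change 7.1 at observed correlation 0.86 (section 8.2; the SD also in section 1.1).
- Baseline IQR 47 to 67 around 53 (section 1.1).
- Alpha: not stated. Two-sided 5% is assumed, and one-sided 5% is shown as the alternative.
- Evaluable per arm: 18 × 0.9 = 16.2, used in the normal approximation; 16 used in the t-test.

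**Step 1: the plan's own figure.** With SD of change 7.1, the standard error of the difference is 7.1 × √(2/16.2) = 2.49, and 7/2.49 = 2.81. Power is Φ(2.81 − 1.96) = 80.1%. The noncentral t with 16 per arm gives 77.0%. One-sided 5% gives 87.7% (normal), so two-sided 5% is the convention that matches the stated figure.

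**Step 2: two readings lead to an SD of change of 7.1.**

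- (a) 7.1 is the SD of change. The 0.5 then plays no part, and the power belongs to the observed pair (7.1, 0.86).
- (b) 7.1 is the SD of a single score. At 0.5 the SD of change is 7.1 × √(2 × (1 − 0.5)) = 7.1, the same number by coincidence.

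An analysis adjusted for baseline does not explain the figure. With score SD 7.1 and correlation 0.5, the residual SD is 7.1 × √(1 − 0.25) = 6.15, and power is 88% (t) or 90% (normal).

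**Step 3: reading (b) against the documents.** Assuming equal variance at both times, the observed pair implies a score SD of 7.1/√(2 × (1 − 0.86)) = 7.1/0.529 = 13.4. A roughly normal score with SD 7.1 would have an IQR 7.1 × 1.349 = 9.6 wide. With SD 13.4 the width would be 18.1. The reported width is 67 − 47 = 20. The IQR is skewed around 53, so this is an order-of-magnitude check, but it fits 13.4 and not 7.1.

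**Step 4: power when the score SD stays at 13.4.** SD of change = 13.4 × √(2(1 − r)).

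| r | SD of change | Power, t, 16 per arm, two-sided 5% | Power, normal, 16.2 per arm, two-sided 5% | Power, normal, 16.2 per arm, one-sided 5% | Difference detectable with 80% power (t, two-sided) |
|---|---|---|---|---|---|
| 0.86 | 7.1 | 77% | 80% | 88% | 7.3 |
| 0.8 | 8.5 | 62% | 65% | 76% | 8.7 |
| 0.7 | 10.4 | 45% | 48% | 61% | 10.6 |
| 0.5 | 13.4 | 30% | 32% | 44% | 13.7 |

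On the two-sided t-test, power falls below 70% once r is under about 0.83, and below 50% once r is under about 0.73.

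**Step 5: sensitivity to the equal-variance assumption.** Let the 4-month SD be k times the baseline SD s, with the SD of change fixed at 7.1 for r = 0.86. Then s = 7.1/√(1 + k² − 1.72k), and the SD of change at r = 0.5 is s × √(1 + k² − k). For k = 0.8 or 1.25 this is 12.7, and power is 33% (t) or 35% (normal). The result hardly moves.

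**The case against.** The strongest reply is that the plan's arithmetic works as written. Section 8.2 gives 7.1 as the SD of the change and says it keeps the same SD; on that reading power is about 80% whatever correlation is named. The 30% comes from holding the score SD fixed instead. The documents never report that SD; it is back-calculated under equal variances. The only observed correlation is 0.86, and nothing in the documents predicts 0.5. Alpha is unstated and the hypothesis is directional, so a one-sided test is conceivable. Finally, 77% is partly an effect of rounding 16.2 down to 16: with 17 per arm the t-test gives 79.6%.

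Much of this stands, as limits on the point. Power of 77 to 80% at 0.86 is no real departure from the plan's figure, and the lower values are conditional scenarios, not the trial's expected power. None of it makes the sentence right. On the literal reading, the 0.5 is an idle input presented as a planning assumption. An SD of change that stays at 7.1 when the correlation is 0.5 requires a score SD of 7.1, which conflicts with the observed pair and the baseline IQR. Moderately unequal variances barely change the result. A one-sided 5% test would give 88% on the literal reading, which is not the stated figure, and still only 42% (t) to 44% (normal) at 0.5.

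Nor is 0.86 assured. It comes from a retrospective cohort treated with retraining, which section 1.1 itself describes as open to bias. The trial adds a chemodenervation arm and uses blinded scoring from video.

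**Conclusion.** The point holds. Section 8.2 does not support 80% power at a correlation of 0.5 with scores as variable as in the earlier cohort. The stated figure is the power at the observed pair, SD of change 7.1 and correlation 0.86. At the correlation the plan names, power would be about 30% (t-test) to 32% (normal approximation), and it is already about 62% to 65% at 0.8. These figures assume two-sided 5%, an unchanged score SD of about 13.4 and equal variance at both times.

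This does not show that the trial is underpowered: if the correlation stays near 0.86, power is close to what is claimed. The error is that the stated assumptions do not yield the stated power, and that the 0.5 looks like a margin but gives none. It should be fixed.

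**What to change.** Replace the power sentence in section 8.2 with text along these lines:

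> In the earlier cohort the SD of the change in SFGS was 7.1 at a pre-post correlation of 0.86, which implies a score SD of about 13.4 if the variance is equal at both times. With a two-sided alpha of 5%, 18 per arm and 10% loss, power for a 7-point difference is about 77% (t-test) to 80% (normal approximation). If score variability is unchanged and the correlation is 0.8, 0.7 or 0.5, the SD of change is about 8.5, 10.4 or 13.4 and power (t-test) is about 62%, 45% or 30%.

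Remove the claim of 80% power at correlation 0.5. If another alpha or a one-sided test was intended, state it and recompute the figures. If 7.1 was meant as the SD of a single score, say so and justify it against the baseline IQR in section 1.1.

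The change is confined to the wording of section 8.2. Sample size, endpoint and model stay as they are, and no patients are added. The cost is a less favourable stated figure.

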8.3. Analysis of endpoints

To reduce the risk of bias, two Department of Surgery research employees will independently grade videos and photos in a blinded fashion using the Sunnybrook Facial Grading System instrument. Video recordings will be presented in random order to two trained research assistants. Ten percent of samples will be included twice to measure intra-rater reliability. Twenty percent of samples will be re-scored by the other rater to measure inter-rater reliability. [name] will be responsible for rater training prior to the investigation, and during the study [name] will provide independent oversight, ongoing training, and resolution of scoring disagreement. At the conclusion of the study, study biostatistician [name], who generated the randomization sequence, will perform data analysis comparing mean changes between groups and account for participant drop out if necessary.

Our qualitative analysis will proceed concurrently with data collection to allow identified themes to be explored in subsequent interviews. In qualitative research this involves both coding the written transcripts and then modeling the coded data. All team members will analyze the data and look for themes and trends that are emergent from the data. For the pre-treatment interviews, we will employ Conventional Content Analysis¹⁵ which will allow us gain direct information from study participants without imposing preconceived categories or theoretical perspectives. For the post-treatment interviews, we will switch to directed content analysis as the findings from pre-treatment interviews will guide our analysis of post-treatment interviews, while capturing emergent themes that come up in the data. We will establish reliability in our analysis through peer debriefing, triangulation, and expert feedback (through [name]), and member checks. Coded transcripts, the codebook, and descriptions of codes will be maintained using NVivo 11 software (QSR International). As coding evolves, changes will be documented in an audit trail. We will map our findings onto the PROMIS measures; specifically, Social

Functioning and Social Isolation scales, to determine the domains that are important to patients but are not included in current quantitative measures.

9. Risks and benefits of trial participation

9.1. Potential risks

Risks associated with treatment

The two approaches to be compared are both widely adopted as standard of care for the treatment of synkinesis. Botulinum toxin shots have risks. These risks include, but are not limited to, infection, bleeding, bruising, weakness, pain where the shot was given, eyelid drooping, headache, nausea, flu like symptoms, dry eyes, skin rash/itching, and the chance the shot may not fully help. The FDA has issued a black box warning for the potential spread of the botulinum toxin from the site the shot was given. Very rare, serious side effects include allergic reactions, body weakness, double vision, speech issues, trouble breathing, abnormal heart rhythm, or a heart attack. While these risks are small, they can happen each time a shot is given.

Neuromuscular retraining therapy: patients may experience common side effects such as increased muscle/joint soreness or pain. There is a risk that their condition will not improve or possibly worsen. There is a risk of other problems, despite all safety measures taken. Certain underlying conditions may increase the risk and severity of problems.

Risks associated with psychological stress

Participants will be discussing their experiences and any adverse outcomes they have experienced. This may cause changes in thought processes and emotion. These changes will mostly be transitory; however they may be recurrent, or even permanent.

Risks associated with loss of confidentiality

There is a risk that information recorded about participants will be shared with people who would not normally have access to this information.

Unknown risks

This study may involve risks to the participant which are currently unforeseeable. We will inform participants as soon as possible if we discover any information that may affect the participant's health, welfare, or decision to be in this study.

9.2. Mitigation of potential risks

Mitigation of risks associated with treatment

Subjects who would have opted to solely undergo neuromuscular retraining therapy may be exposed to risks of chemodenervation if they are randomly assigned to that procedure. These risks are described in detail to the patient as part of the informed consent process for treatment. Botox injections will be conducted according to standard clinical procedures. Subjects are not seen between Botox treatments, but they are instructed to call with any concerns, questions, or adverse reactions. Patients who are capable of carrying a fetus will be asked before each injection if they are pregnant.

Mitigation of risks associated with psychological stress

The participant showing signs of psychological stress will be reminded of the voluntary nature of the clinical trial they are participating in, and that they can stop at any time without punishment or loss of care. The Primary Investigator will be made aware of any participants displaying these signs by the research staff, and will refer them to appropriate resources as needed.

We are using the HADS and BIPQ questionnaires only for research, not to diagnose mental health issues. We will not tell patients the results. We will advise patients to contact their physician or other health care provider, such as a mental health professional, if they are experiencing emotional distress.

If imminent harm to self or others is identified from participation in the study, patients' responses and health information may be shared with others (e.g., mandatory reporting to authorities or physicians).

Mitigation of risks associated with loss of confidentiality

All information obtained and associated data files will be confidential and will be kept in a locked file or password protected computer. The risk of breach of confidentiality regarding participation in the study outside of the scope of the research will be handled by carefully controlling access to study data only to personnel on the research team.

Confidentiality will be protected further by: (1) using a participant log form that contains only the minimum necessary protected health information (PHI) concerning participants, and storing this log in a locked area when not in use, (2) not sharing PHI with any outside institution, (3) coding data collection forms with a consecutive participant number that is not derived from any participant personal identifiers, and linking that data collection form to the participant log, and (4) storing the participant log and data collection forms separately.

It is highly likely that these measures will result in avoidance of breach of confidentiality outside of the research. In addition, the data to be collected are not sensitive to participants. A data and safety monitoring board will also be in place.

9.3. Potential benefits and risk-to-benefit ratio

Potential benefits to the individual participant

Individual benefits to participants are not guaranteed, as this study is seeking to determine which of the two accepted standard of care treatments participants could receive will yield the best clinical benefits.

Potential benefit to society

We will gain scientific and clinical understanding of impaired facial mobility caused by synkinesis with regard to social functioning and quality of life, allowing us to understand the devastating effects of synkinesis that require clinical attention. Further, this work will explore the efficacy of neuromuscular retraining therapy for patients with synkinesis, thus closing a critical gap in knowledge concerning efficacious treatments for this condition. Finally, this work leverages the volume of patients seen at the University of Wisconsin Facial Nerve Clinic, and is significant in its prospective randomized design to measure therapy against established chemodenervation effects.

In addition, our unique qualitative data analysis, could potentially lead to the development of a novel way for clinicians and researchers to measure symptoms and outcomes in patient populations. This could lead to more patient-centered care. It could also reduce the need to administer other instruments, which can be time-consuming and may miss important indicators of disease status and well being.

Risk-to-benefit ratio

Although individual benefits to participants are not guaranteed, it is anticipated that considerable societal benefit will result from the proposed studies. Currently both management approaches proposed are accepted standards of care. The reason this study is essential is that currently the evidence cannot support one treatment over another and therefore we feel that this study has true equipoise. The

results of this study can be used to help guide the treatment of synkinesis and help provide solid evidence to support future guidelines.

10. Adverse events and unanticipated problems

10.1. Adverse event definitions

Adverse event (AE)

An adverse event is defined as any untoward or unfavorable medical occurrence in a human participant including any abnormal sign, symptom, or disease temporally associated with the participant's participation in the research, whether or not considered related to the participant's participation in the research. Adverse event collection will begin at Day of Treatment Onset and continue through the last assessments. Untoward medical occurrences or acute conditions that occur between screening and surgery will be recorded as medical history.

Serious adverse event (SAE)

A serious adverse event is defined as any adverse event that meets one of the following criteria:

- Results in death; OR
- Is life-threatening; OR
- Requires hospitalization or prolongs existing hospitalization; OR
- Results in significant or persistent disability or incapacity; OR
- Results in a congenital anomaly/birth defect; OR

Unanticipated problem (UP)

An unanticipated problem is defined as an event that meets all of the following criteria:

- (1) unexpected in severity, nature, or frequency given the research procedures and the characteristics of the participant population (i.e., problems that are not described in this protocol or other study documents); AND
- (2) related or possibly related to participation in the research; AND
- (3) suggests that research places participants or others at a greater risk of harm related to the research than was previously known or recognized.

10.2. Severity assessment and Grade

The severity of all adverse events will be assessed according to the following scale:

- Mild = does not interfere with the participant's usual function
- Moderate = interferes to some extent with the participant's usual function
- Severe = interferes significantly with the participant's usual function

The grade is assessed according to the Common Terminology Criteria for Adverse Events (CTCAE), Version 5.0.

- Grade 1: Mild; asymptomatic or mild symptoms; clinical or diagnostic observations only; or intervention not indicated.
- Grade 2: Moderate; minimal, local or noninvasive intervention indicated; or limiting age-appropriate instrumental activities of daily living (e.g. preparing meals, shopping for groceries or clothes, using the telephone, managing money, etc.)
- Grade 3: Severe or medically significant but not immediately life-threatening; or hospitalization or prolongation of hospitalization indicated; or disabling; or limiting self-care activities of daily living (e.g. bathing, dressing and undressing, feeding self, using the toilet, taking medications, not bedridden, etc.)
- Grade 4: Life-threatening consequences; or urgent intervention indicated.

- Grade 5: Death related to AE.

10.3. Causality assessment

The PI will determine the relationship of adverse events to the research intervention using the following scale:

- Definite = AE is clearly related to the study procedures
- Probable = AE is likely related to the study procedures
- Possible = AE is possibly related to the study procedures
- Unlikely = AE is doubtfully related to the study procedures
- Unrelated = AE is clearly not related to the study procedures

